6.0 Study Endpoints

6.1 The primary endpoints in the proposed study are: 1) the level of cognitive functioning (as measured by the neuropsychological tests and self-reported cognitive functioning using the PAOFLI)

Secondary endpoints are: 1) Circadian activity rhythms using an actigraph (a small device similar in size to a watch that measures sleep and wake activity); 2) The Pittsburgh Sleep Quality Index; 3) the FACIT Fatigue Scale; 4) Quality of Life measured by the SF-36 scale; 5) a Credibility/Expectancy Questionnaire; 6) levels of Inflammatory Immune Markers; 7) the amount of time that the light boxes are used; 8) treatment satisfaction using the FACIT-TS-G scale; 9) depressed mood as measured by the CES-D; and 10) neurobehavioral functioning as measured by the Frontal Systems Behavior Scale.

6.2 With regard to safety endpoints, there are no known risks associated with the use of the light boxes in the treatment of cognitive impairments. However, we will monitor those who decide to cease treatment because they find the treatment approach unacceptable along with their concerns regarding treatment.

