- 5) **Cognitive Screening (Screening):** Participants will be asked whether they have concerns about their cognition by asking a question derived from the two cognitive questions on the

PROTOCOL TITLE: Treating cognitive impairments in cancer patients via systematic light exposure

European Organization for Research and Treatment of Cancer Quality of Life Questionnaire (EORTC QLQ C-30).

- 6) **Neuropsychologically-assessed Cognitive Functioning (Times 1, 3, and 4):** Standardized neuropsychological tests will be used to evaluate multiple cognitive domains. They include all of the tests recommended by the International Cognition and Cancer Taskforce in their Lancet article⁶ chosen due to their frequent use in CRCI assessment and appropriateness for repeat assessments over time: a) Premorbid Intellectual Function will be assessed using the Wechsler Test of Adult Reading and the Vocabulary subtest of the Wechsler Adult Intelligence Scale - 4th Ed. (WAIS-IV) at Baseline only; b) Psychomotor vigilance will be assessed with the Psychomotor Vigilance Task; c) Attention will be assessed with the Digit Span subtest of the WAIS-IV;⁹⁹ d) Visual motor performance will be assessed with the Grooved Pegboard Test and Block Design subtest of the WAIS-IV; e) Visuospatial ability will be assessed with the Rey Complex Figure Test. f) Sustained attention and vigilance will be assessed with the Conners Continuous Performance Test 3rd Edition will be used to assess sustained attention and vigilance; g) Information processing will be assessed with Trail-Making Test A.¹⁰⁰ h) Processing speed will be measured with the Coding subtest of the WAIS-IV; i) Verbal fluency will be assessed with the Verbal Fluency subtest of the Delis-Kaplan Executive Function System (D-KEFS). j) Verbal learning and Memory will be assessed with the Hopkins Verbal Learning Test - Revised.¹⁰² k) Visual learning and memory will be assessed with the Brief Visuospatial Memory Test – Revised. l) Executive Function will be assessed with Trail-Making Test B¹⁰⁰ and the Paced Auditory Serial Addition Task¹⁰³ and the Stroop Color and Word Test.

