patients used the light box about 50% of the required days. This usage frequency was sufficient for cognitive improvement to occur in the BWL group. A 50% level of adherence will be considered acceptable in this study. Acceptability: As recommended in the literature, in addition to accrual rates, we will assess acceptability by evaluating participants' comments about the intervention after they have had experience with it.¹¹³ Finally, a comparison of the BWL and DRL on the FACIT-TS-G will be conducted using t-tests. Significant differences in favor of the BWL condition are expected.

Aim 2: Examine whether BWL compared with DRL among HSCT survivors suffering from cognitive impairment yields significant improvements in cognitive functioning. We will examine the cognitive functioning subscales and composite scores in separate analyses. Linear mixed model analysis with repeated measures will be conducted using the SAS procedure MIXED.

Contrasts will compare groups across assessments. The linear mixed model approach has a range of choices for the error variance/covariance structure and accommodates missing data thus protecting against a "completers only" bias. Since multiple outcomes will be correlated with one another, *p*-values for significance will be Sidak-adjusted for multiple comparisons. If there is variation in light box utilization, we will use duration time as a predictor of the outcome measures as in Aim 1. No pre-intervention bias favoring BWL over DRL is anticipated. However, we will test this assumption by crossing expectancy with the treatment condition. This interaction is not expected to be significant. These results will determine preliminary efficacy and sustainability of the intervention.

Power: Based on [name]'s pilot study with 10 breast cancer patients, the effect size indicated that we would need a sample size of 19 to achieve power at 0.80. However, the sample size is likely too small to provide reliable estimates of improvement in cognitive functioning. One of the main aims is to determine preliminary efficacy of the intervention in preparation for a larger scale trial. For a total sample of 80, we calculated the mean difference between the two treatment arms for the Neurocognitive (composite) Index and assumed a repeated measures design with an autoregressive lag 1 error structure and autocorrelation of 0.60. The difference able to be detected with power equal to 0.80 and alpha = 0.05, is 0.209.

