9.2 Power analyses

Aim 1 Power: Based on [name]'s pilot study with 10 breast cancer patients, the effect size indicated that we would need a sample size of 19 to achieve power at 0.80. However, the sample size is likely too small to provide reliable estimates of improvement in cognitive functioning. One of the main aims is to determine preliminary efficacy of the intervention in preparation for a larger scale trial. For a total sample of 80, we calculated the mean difference between the two treatment arms for the Neurocognitive (composite) Index and assumed a repeated measures design with an autoregressive lag 1 error structure and autocorrelation of 0.60. The difference able to be detected with power equal to 0.80 and alpha = 0.05, is 0.209.

Aim 2 Power: Our preliminary R-21 study that examined BWL vs. DRL on cancer-related fatigue in a mixed cancer population (including HSCT) provided guidance for the power. Sleep Quality: While survivors in the BWL group had better sleep quality scores than the DRL group, the main effect for treatment was not statistically significant, no doubt due to sample size. Cohen's d was 0.63. For a repeated measures design with alpha equal to 0.05 and a sample size of 40 per group, power=0.99. CAR: There was significant time x treatment interaction (p=0.02) on the F statistic. We calculated power for a repeated measures design with autoregressive lag 1 structure and autocorrelation of 0.60. With alpha equal to 0.05 and sample size of 40 per group, power=0.99. Fatigue: As with CAR, there was significant time x treatment interaction (p=0.003). Using the same method as above, power = 0.99. Depressed mood: There was a significant (p=0.004) time x treatment interaction. Using the same method as above, power = 0.99.

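### The 80% power for the Neurocognitive composite is stated at alpha 0.05, but the Sidak rule as written also covers the composite; under single-step Sidak with two tests the power would be about 71%.

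*Combined protocol and SAP*

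**What the plan says.** In 9.1, Aim 2, the plan states: "We will examine the cognitive functioning subscales and composite scores in separate analyses". A few sentences later, because the outcomes are expected to be correlated, p-values "for significance will be Sidak-adjusted for multiple comparisons". The Aim 2 paragraph ends: "These results will determine preliminary efficacy and sustainability of the intervention".

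The power text that follows concerns one outcome only. For a total sample of 80, "we calculated the mean difference between the two treatment arms for the Neurocognitive (composite) Index" (wording from 9.2), assuming a first-order autoregressive error structure with autocorrelation 0.60. The result is: "The difference able to be detected with power equal to 0.80 and alpha = 0.05, is 0.209". Section 9.2 repeats this under the label Aim 1 Power. Neither place mentions the Sidak adjustment.

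No section lists the outcomes in the Sidak family, gives k, says whether the procedure is single-step or step-down, or places the composite outside it. Section 6.1 does not settle the matter. It defines the primary endpoint as cognitive functioning "as measured by the neuropsychological tests and self-reported cognitive functioning using the PAOFLI", without naming the composite as the one primary outcome. Section 7.3, item 6, describes a battery covering many domains, but the plan does not define which scores are the subscales.

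**The concern.** The plan gives one alpha for judging the composite and, apparently, another for computing its power. The only outcomes named ahead of the Sidak sentence are the subscales and the composite scores, so the natural reading puts the composite in the adjusted family. Power computed at 0.05 then overstates the chance that the composite reaches significance under the plan's own rule.

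What is at stake is the significance statement on preliminary efficacy, and how a null result on the composite would be read. With k undefined, the number of tests and the treatment of the composite also stay open until results are known. The adjustment acts on p-values only. It does not change the effect estimates or SDs that the larger trial would be planned on.

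**Working it through.** **Inputs.** From 9.1 and 9.2: power 0.80, alpha 0.05, detectable difference 0.209, total N 80, autocorrelation 0.60. Allocation of 40 per group comes from the power text for sleep and fatigue in the same sections. Neuropsychological testing takes place at three time points (7.3, item 6). Two-sided testing is assumed, because sidedness is not stated.

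**1. The plan's own figure.** The usual formula is MDD = (z₀.₉₇₅ + z₀.₈₀) × SD × √(2v/n). For a time-averaged comparison over three points, v = (3 + 2(0.6 + 0.6 + 0.36))/9 = 0.68. With n = 40 this gives 2.802 × √(2 × 0.68/40) = 0.517 SD. Change-from-baseline, baseline-adjusted and generalised least squares variants give 0.47 to 0.71 SD. The plan states neither the SD nor the units of the composite, so 0.209 can be neither reproduced nor refuted. It would imply an SD of about 0.30 to 0.44 across these variants. From here on, the stated 80% at 0.05 is taken as given.

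**2. Power at the adjusted alpha.** The Sidak per-test level is α_k = 1 − 0.95^(1/k). The noncentrality is fixed by the plan's claim: 1.960 + 0.842 = 2.802. Power is then Φ(2.802 − z at 1 − α_k/2), and no SD is needed. For k=2, α = 0.0253, z = 2.237, and Φ(0.565) = 0.714. A noncentral t with 78 df, anchored in the same way, gives 0.710. The detectable difference at 80% power is 0.209 × (z + 0.842)/2.802.

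| k | α_k | Power at 0.209 (t / normal) | Detectable difference (normal) |
|---|---|---|---|
| 1 | 0.0500 | 80% / 80% | 0.209 |
| 2 | 0.0253 | 71.0% / 71.4% | 0.230 |
| 3 | 0.0170 | 65.4% / 66.1% | 0.241 |
| 5 | 0.0102 | 58.2% / 59.2% | 0.254 |
| 12 | 0.0043 | 46.2% / 47.8% | 0.276 |

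At k=2, keeping 80% power at 0.209 would need 40 × (3.078/2.802)² ≈ 48.3, so 49 per arm. One-sided and F-test versions at k=2 give 70.3% to 71.4%.

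The smallest family on the plain reading is k=2: one composite and one subscale. The other values of k are assumptions. For example, k=12 counts the eleven domains tested repeatedly in 7.3 (items b to l) plus one composite, and the plan does not say that this is the family.

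**3. Step-down Sidak.** At k=2 the composite is significant if it passes 0.0253, or if the other outcome passes 0.0253 and the composite then passes 0.05. Simulation (2 million draws per setting, composite noncentrality 2.802, assumed correlation 0.3 to 0.7) gives about 71.5% when the other outcome has no effect, 76% to 77% when its effect equals the composite's, and close to 80% when its effect is very large.

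**The case against.** A reader might infer from the k=2 row that power is at most 71%, or that the risk of missing a difference of 0.209 is at least 29%. The documents do not support either as a bound. They say only that p-values are Sidak-adjusted. A step-down version fits those words and loses less. So would a version that allows for the correlation which the plan gives as its reason for adjusting: with α = 1 − 0.95^(1/k^(1−r)) and an assumed r of 0.5, the level at k=2 is 0.0356 and power is about 76%.

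A second objection goes further. The plan powers only the composite, at 0.05, and speaks of separate analyses. That is compatible with the composite as lead test and Sidak applied among the subscales alone, in which case the 80% is correct. This possibility stands. It is not written anywhere, however, and fitting separate models does not by itself take a test out of a multiplicity family.

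Third, this is a feasibility and preliminary-efficacy study with no stated go/no-go rule tied to significance of the composite, and a larger true effect would lose little. If the 0.33 SD pilot difference in 2.2 were on the same scale as 0.209 (an assumption), power at k=2 would be Φ(2.802 × 0.33/0.209 − 2.237) ≈ 99%. This limits the consequence. It does not reconcile the two alphas, and the power section itself regards the pilot as probably too small for reliable estimates.

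**Conclusion.** The mismatch is real: the multiplicity rule, as written, covers an outcome whose power was computed without it. On the plain reading the stated 80% is too high. Under single-step Sidak it becomes about 71% at k=2 and falls further as k grows, for example to 58% to 59% at k=5.

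These sizes rest on three things: the plan's own 80% at 0.05, which cannot be checked; two-sided testing with 40 per arm; and a k that the plan does not state. With step-down Sidak at k=2 the figure would lie between about 71.5% and just under 80%. With the composite outside the family, there is no loss. That the family is undefined is firmly established; the exact loss of power is not. The point should be corrected, but it does not put the design or the planning estimates in doubt.

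**What to change.** Before outcome data are analysed, amend 9.1 and 9.2 so that the alpha in the power statement is the alpha at which the composite will be judged.

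**Preferred.** Keep the composite in the family. List the outcomes and group contrasts that make up the family, give k, say whether Sidak is single-step or step-down, and restate the power or the detectable difference at the adjusted alpha. No new data or visits are needed. The cost is a rerun of the power calculation and a less favourable stated figure.

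**Alternative.** State that the composite is the single efficacy test at two-sided 0.05 on a named contrast, and apply Sidak only to the remaining cognitive outcomes. The plan must then say that those outcomes do not by themselves carry the efficacy claim. Otherwise two separate 5% allowances could give a family-wise error of up to about 10% (1 − 0.95² = 0.0975 if independent). This keeps the 80% figure but changes the order of endpoints in 6.1, where the self-report scale now sits within the primary endpoint. It is therefore a sponsor decision and more than a wording change.

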1.2 Hypotheses

- Hypothesis 1: BWL treatment will be feasible and acceptable in autologous and allogeneic HSCT survivors.
- Hypothesis 2: Auto-HSCT and allo-HSCT survivors receiving BWL will have greater improvement in cognitive functioning than those receiving DRL.
- Hypothesis 3: The relationship between BWL and CRCI will be mediated by CAR and sleep.

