Following the Time 1 assessment, participants will be instructed to self-administer light treatment for 30 minutes every morning for 4 weeks. Participants will be informed that "The Litebook is a compact portable lamp (approximately 5" x 5" x 1") and weighs less than a pound. It is very easy to use. The Litebook is directed toward the eyes for 30 minutes each morning in order to trigger light receptors in the retina to trigger a cascade of messages throughout the body. It is powered by a rechargeable lithium-ION battery which we provide and can also be connected to a power source." As indicated in the consent form, participants will be told that they will receive one of two different light boxes of different wavelengths that are being tested (i.e., the same light box but with different bulbs to emit different wavelengths). The 30 minute dose is used in the treatment of seasonal affective disorder and has been shown to have a low risk of side-effects. For participants who require assistance, we will work with a caregiver to ensure correct actigraph and light box

PROTOCOL TITLE: Treating cognitive impairments in cancer patients via systematic light exposure

use. The assessment schedule and data analytic plan will allow us to address the Specific Aims. To increase the likelihood of adherence, email reminders will be sent to participants to use the light boxes and complete sleep and Litebook logs.

Litebook devices can only emit one wavelength – either BWL or DRL – but they are identical in all other ways. BWL Litebook emits approximately 1000 lux and the DRL Litebook emits < 50 lux. Safety precautions are the same for both as indicated by the research outlined below.

Use of Litebook in Previous Research

[name] and colleagues' (2014) investigated BWL to treat cancer-related fatigue in cancer survivors (including HSCT) using the same Litebooks for the current study. BWL was found to be more effective in reducing cancer-related fatigue than DRL. There were no safety concerns nor adverse events. This study was approved by Mount Sinai's IRB in 2011.

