9.0 Data and Specimen Management

9.1 Data analysis plan

Descriptive statistics will be calculated for the entire group and separately for each treatment group. T-tests and Fisher's exact tests will be used to assess group differences at baseline for possible confounders (i.e., demographic variables, and clinical characteristics *including time since transplant*). Variables showing differences between the two groups will be used as covariates in subsequent analyses. Since there is no known seasonality effect on cognitive functioning, seasonality will not be controlled in these analyses.

Aim 1: Assess the feasibility and acceptability of BWL as an intervention for CRCI in HSCT survivors. Feasibility: We will adhere to currently accepted practice for feasibility studies¹¹⁰ by measuring the number of eligible patients, willingness of participants to be randomized, follow-up rates, the number who cease the intervention and their specific concerns about the intervention. We will monitor adherence by examining integrated meter data (i.e., time and duration of light box use). We expect high adherence, but if there is variation in duration, we will use duration as a predictor of the outcomes. Participants will be asked to log light box use (beginning and ending time) and reasons for not using it if that occurs. There is no gold standard for what constitutes a “feasible” study and relevant CRCI intervention feasibility studies have not been home-based.^{18, 111} Nevertheless, in an inpatient cognitive rehabilitation study of HSCT patients, 78% completed baseline, intervention, and time 2 assessments.¹⁸ A light exposure feasibility study for seasonal affective disorder deemed a 68% completion rate as acceptable,¹¹² and this is the criteria we will use in this study. In [name]'s pilot study, breast cancer

PROTOCOL TITLE: Treating cognitive impairments in cancer patients via systematic light exposure

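### Aim 2 lets light-box duration, metered after randomisation, into the BWL versus DRL analysis; the arm estimate could be biased if use differs by arm

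*Combined protocol and SAP*

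**What the plan says.** Section 9.1, Aim 2, specifies a repeated-measures linear mixed model for the cognitive scores. "Contrasts will compare groups across assessments", and p-values get a Sidak adjustment. The next rule is "If there is variation in light box utilization, we will use duration time as a predictor of the outcome measures as in Aim 1". An expectancy check follows, and the paragraph ends: "These results will determine preliminary efficacy and sustainability of the intervention".

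The cross-reference leads to the adherence text under Aim 1, which states the same rule without a model: "if there is variation in duration, we will use duration as a predictor of the outcomes".

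Duration comes from the meter in the light box during the exposure period (section 7.3, item 17). Time of use is also secondary endpoint 7 (section 6.1).

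The plan does not say:
- whether duration joins the BWL versus DRL model or a separate analysis;
- whether it would interact with visit or arm;
- how much variation triggers the rule;
- whether an analysis by assigned arm without duration is the main one.

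On the contrast itself, Hypothesis 2 (section 1.2) says that BWL recipients "will have greater improvement in cognitive functioning than those receiving DRL", which points to arm-by-visit. The Aim 2 power statement says "we calculated the mean difference between the two treatment arms for the Neurocognitive (composite) Index", which can be read as an arm difference averaged over visits.

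**The concern.** Randomisation protects a comparison of the arms as assigned. Use of the box happens afterwards and may reflect motivation, fatigue or tolerance of the light, which may also bear on cognition. If the arms differ in mean use, a model that holds duration fixed compares BWL and DRL participants who are no longer alike in those respects. If use itself affects cognition, the model also removes part of the effect under study.

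Aim 2 is meant to supply the efficacy estimate for a larger trial. As written, the role of duration could be settled after the data are seen.

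**Working it through.** **Plan's own figure.** The plan gives no figure for this point. The only one for the Aim 2 contrast is the detectable difference of 0.209, which has no stated unit or SD. With 40 per arm, three visits and AR(1) correlation 0.60, the averaged arm contrast has SE = sqrt((2/40) × (3 + 4×0.6 + 2×0.36)/9) = sqrt(0.05 × 0.68) = 0.184 SD. The detectable difference is then 2.80 × 0.184, about 0.52 SD. This equals 0.209 only if the composite SD is about 0.40. The figure is not disputed here and serves only to mark the scale.

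**Trigger.** Participants "self-administer light treatment for 30 minutes every morning for 4 weeks", which is 28 sessions. In the pilot, "patients used the light box about 50% of the required days". If everyone had the same 50% daily chance of use, days used would still have an SD of sqrt(28×0.5×0.5) = 2.65. At a 95% chance it is sqrt(28×0.95×0.05) = 1.15. Read literally, the condition would be met by chance scatter alone.

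**Set-up (all inputs below are assumptions except the AR(1) value and the visits).** Use is D = a·T + u1·U + e, where T is arm, U is a shared factor, and D has within-arm SD 1. The outcome at Times 1, 3 and 4 has SD 1, residual AR(1) 0.6 and no treatment effect. U loads u2 = 0.5 on outcome, either at all visits or only after baseline. The arm gap a runs from 0 to 0.5 SD and u1 from 0.5 to 0.7.

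The slope of outcome on use within arm is u1×u2 = 0.25 (0.35 when u1 = 0.7) wherever U acts. Conditioning on D shifts an arm contrast by −a × (the duration coefficient fitted for that contrast):

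- *Duration as main effect.* There is one common coefficient. AR(1) weights over the visits are 1 : 0.4 : 1. It is 0.25 if U acts at all visits, and 0.25×(0.4 + 1)/2.4 = 0.146 if only after baseline. Each visit's arm difference moves by the same amount, so arm-by-visit differences do not move.
- *Duration-by-visit terms.* The arm-by-Time 3 contrast uses slope at Time 3 minus slope at Time 1: 0.25 − 0.25 = 0, or 0.25 − 0 = 0.25.
- *Baseline-adjusted at Time 3.* If U acts at all visits, the Time 1–Time 3 correlation is 0.25 + 0.75×0.6 = 0.70 and the coefficient is 0.25×(1 − 0.70)/(1 − 0.0625) = 0.08. If only after baseline, it is 0.25.

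Size of shift in outcome SDs:

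| Model and contrast | U acts | a=0.1 | a=0.3 | a=0.5 | a=0.5, u1=0.7 |
|---|---|---|---|---|---|
| Main effect; arm difference at a visit or averaged | all visits | 0.025 | 0.075 | 0.125 | 0.175 |
| Same | after baseline | 0.015 | 0.044 | 0.073 | 0.102 |
| Main effect; arm-by-visit | either | 0 | 0 | 0 | 0 |
| Duration-by-visit; arm-by-Time 3 | all visits | 0 | 0 | 0 | 0 |
| Same | after baseline | 0.025 | 0.075 | 0.125 | 0.175 |
| Baseline-adjusted, Time 3 | all visits | 0.008 | 0.024 | 0.040 | 0.060 |
| Same | after baseline | 0.025 | 0.075 | 0.125 | 0.175 |

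Simulation with 200,000 per arm agrees within about 0.002 in every cell. All shifts are zero at a = 0. They are negative if BWL users use the box more and positive if DRL users do. With u1 = 0.7 the largest shift at the smaller gaps is 0.1×0.35 = 0.035 and 0.3×0.35 = 0.105.

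**Direct effect of use (a separate set of assumptions).** Suppose use adds 0.3 SD per SD of use, and a shared factor has loading 0.4 and correlation 0.5 with use. The slope after baseline is 0.3 + 0.5×0.4 = 0.5. With duration-by-visit terms and a gap of 0.5, the shift is −0.25, so a true 0.33 SD is estimated as 0.08. The model without duration stayed within 0.01 of the truth in every setting.

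**Missing visits.** Suppose 32% lack Times 3 and 4 (the complement of the 68% completion criterion under Aim 1). The arm-by-visit contrast with duration as a main effect then moves by at most 0.001 SD if data are missing at random, and by 0.012 SD if low users drop out more.

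**The case against.** The strongest reply is that duration was never meant to enter the efficacy model. Where the plan wants adjustment it speaks of covariates or of controlling for something (baseline imbalances in section 9.1, physical health and phase advance in section 7.3). Duration is only called a predictor. The rule originates in the adherence text of Aim 1 and appears in Aim 2 after the model, contrasts and multiplicity rule, beside another supplementary check. That reading is fair and may be what the authors intend. But the rule sits between the group contrasts and the sentence saying these results determine efficacy, and nothing confines it to a separate analysis.

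Second, equal use is plausible. Section 7.1.1 describes devices that differ only in the light emitted. Against that, the plan expects higher satisfaction with BWL (section 9.1), and persistent side effects end the intervention (section 10.1). Neither gives a figure for use by arm.

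Third, most of the plan points to the less affected contrast: Hypothesis 2 concerns improvement, and the power statements for circadian rhythms, fatigue and depressed mood rest on time-by-treatment interactions. This stands, and it limits the concern. It does not remove it, because duration-by-visit terms are not excluded and the main contrast is not named.

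Fourth, the variation that triggers the rule may mean a substantial departure from the high adherence the plan expects, not chance scatter. That is also a fair reading, but no threshold is given.

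**Conclusion.** The concern holds in conditional form. The text permits the BWL versus DRL estimate to be conditioned on a variable measured after randomisation. Bias then requires two further things: mean use must differ by arm, and use must be related to outcome directly or through a shared cause.

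Under the shared-cause assumptions, the forms that can shift move by about 0.01 to 0.025 SD at a 0.1 SD gap (correlation with use 0.5) and by up to about 0.18 SD at a 0.5 SD gap. The pilot difference in section 2.2 was 0.33 SD. No trial data bear on which gap is realistic.

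A reader might infer that the Aim 2 estimate will be biased, or that the plan commits to adjusting for duration. The documents support neither: they do not assign duration to the arm model, and several readings give no shift. Nor do they support a general claim of inflated false positives. For the averaged contrast, a normal approximation gives 5.0% at a gap of 0 and about 5.2% at 0.1. The 15.2% found by simulation belongs to the single most extreme setting (gap 0.5, correlation with use 0.7, shared factor at all visits).

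The point should be acted on because the better method is clear and nearly free.

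**What to change.** In section 9.1, Aim 2, state that the main efficacy model compares all randomised participants by assigned arm, with baseline covariates only and without duration. Name its main contrast: arm-by-visit, in line with Hypothesis 2. Move the duration rule to a separate use-response analysis, labelled exploratory, with within-arm slopes or an arm-by-duration term. A short note could say that the same separation applies wherever other aims reuse this model.

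The cost is a few sentences in the plan and one extra exploratory table. The same data are analysed, and nothing changes in conduct or sample size.
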